### 7.1/ Vital signs

Heart rate, Blood Pressure, Respiratory rate, Pulse oximetry, Core temperature (esophageal or rectal, temperature sensing bladder catheters, or pulmonary artery catheters, if present). All vital signs will be measured by standard of care and recorded as per study data collection requirements.

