## 8/ Study Interventions

### Temperature management:

1. Therapeutic Hypothermia Arm: The participating ICUs share an established institutional protocol for NMB and TH, which will facilitate rapid mobilization of treatment following randomization. Sedation will be adjusted to achieve a RASS -4 score and cisatracurium (Nimbex™) will be initiated and adjusted to the lowest rate that achieves nerve stimulation response of 2 twitches in train-of-four monitoring, reduction in ventilator dyssynchrony to acceptable levels, and elimination of shivering. NMB will be continued through the rewarming phase at least until core temperature reaches 35.5°C (~54h total time). Note that if the supply of Nimbex in the Clinical Pharmacy is insufficient to treat the subject, a supply of study-only Nimbex is available in the Investigational Drug Service Pharmacy.

Since the objective of CHILL-pilot is to test the effectiveness of cooling to a target temperature rather than the performance of a specific cooling device, patients in the TH arm will be cooled using one of the institution's two FDA-approved surface cooling devices, Blanketrol II cooling blankets or Arctic Sun™ cooling system. Core temperature will be reduced to 34°-35°C as quickly as possible and TH maintained for 48h. Patients will then be rewarmed to 36°C by 0.3°C/h and the cooling device removed. Post-cooling fever suppression is not part of the CHILL-pilot protocol. Cooling parameters were selected to optimize risk:benefit ratio. The criteria for early termination of hypothermia are persistent severe bradycardia (heart rate < 30 associated with mean arterial pressure <65 without vasopressor agents), uncontrolled bleeding, and intractable ventricular arrhythmias.

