- Indicate whether patient was started on renal replacement therapy (RRT) since randomization by checking appropriate “Yes/No” box on line 16. If the patient was already receiving RRT, check the N/A box.
- If the patient was already receiving RRT, indicate whether it was discontinued since randomization by checking appropriate “Yes/No” box on line 17. If the patient was not previously receiving RRT, check the N/A box.
- On line 18, please if indicate if any of the adverse events occurred since randomization by checking the appropriate “Yes/No” boxes.
- Enter the lowest and highest values since randomization from the EMR for systolic and diastolic blood pressure and mean arterial pressure in mm Hg in the appropriate fields on line 19. Record the lowest and highest values for CVP in cm H2O. If no CVP measurements check the “CVP not available” box. If only one measurement for any of the vital signs, enter the value in the “Lowest” CVP box and check the “Single” box.
- On line 20, record date and time of randomization and initiation of cooling or check “Not cooled” box if patient was not cooled.

- In the table on line 21, check the box for the time period when patient was randomized. Then for each 2-hour period beginning with randomization and continuing until 0800 on the day after randomization the highest and lowest recorded core temperatures, check the box indicating the location of the temperature probe, and enter the lowest recorded SpO2 value, the corresponding FiO2, and the most concurrently measured Mean Airway Pressure. If there is only a single temperature measurement during the period, record in the “Lowest” field and check the “Single value” box. If there are no SpO2 measurements during a 2-hour period, indicate by checking the “None” Box for SpO2. If the patient was receiving supplemental oxygen by NC, calculate the FiO2 using the formula:  $FiO_2 = 0.21 + 0.03 \times \text{flow rate in LPM}$ .
- Indicate whether the patient received corticosteroids since randomization by checking the appropriate “Yes/No” box on line 22. If “Yes,” enter the total dose in hydrocortisone equivalents using the conversion, 1 mg prednisone or methylprednisolone = 4 mg hydrocortisone and 1 mg dexamethasone = 25 mg hydrocortisone.

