- If the patient was already receiving RRT, indicate whether it was discontinued in the past 24 hours by checking appropriate “Yes/No” box on line 16. If the patient was not previously receiving RRT, check the N/A box.
- On line 17, please if indicate if any of the adverse events occurred in the last 24 hours by checking the appropriate “Yes/No” boxes.
- Enter the lowest and highest values since randomization from the EMR for systolic and diastolic blood pressure and mean arterial pressure in mm Hg in the appropriate fields on line 15. Record the lowest and highest values for CVP in cm H2O. If no CVP measurements check the “CVP not available” box. If only one measurement for any of the vital signs, enter the value in the “Lowest” CVP box and check the “Single” box.
- In the table on line 19 enter for each 2-hour period in the previous 24 hours the highest and lowest recorded core temperatures, check the box next to the location of the probe, and enter the lowest recorded SpO2 value, the corresponding FiO2, and the most concurrently measured Mean Airway Pressure. If there is only a single temperature measurement during the period, record in the “Lowest” field and check the “Single value” box. If there are no SpO2 measurements during a 2-hour period, indicate by checking the “None” Box for SpO2. If the patient was receiving supplemental oxygen by NC, calculate the FiO2 using the formula:  $FiO_2 = 0.21 + 0.03 \times \text{flow rate in LPM}$ .
- Indicate whether the patient received corticosteroids in the last 24 hours by checking the appropriate “Yes/No” box on line 20. If “Yes,” enter the total dose in hydrocortisone equivalents using the conversion, 1 mg prednisone or methylprednisolone = 4 mg hydrocortisone and 1 mg dexamethasone = 25 mg hydrocortisone.
- Indicate whether the patient received an inhaled vasodilator in the last 24 hours by checking the appropriate “Yes/No” box on line 21. If “Yes,” indicate which agent by checking the appropriate box and recording the total number of hours the at least one agent was administered.
- Indicate if the patient received vasopressor support at any time since randomization by checking the appropriate “Yes/No” box on line 22. If “Yes,” check the box next to each of the agents that was received, the highest infusion rate (and units) received, and the total hours receiving any vasopressor support. If “No” skip to question 23.

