 Intractable ventricular arrhythmia  Decision of ICU provider  Decision of family

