### Skip to question 15.

If in the Control arm, received therapeutic hypothermia in last 24 hrs?  Yes  No  N/A

Still intubated or receiving Assisted Breathing?  Yes  No  N/A

If "No," when was patient extubated or UAB for ≥48 hours?            
MONTH D D Y Y Y Y TIME (0-2400)

Was RRT started since randomization?  Yes  No  N/A

If RRT had been previously initiated has it stopped since randomization?  Yes  No  N/A

Since randomization did the patient have any of the following:

Bradycardia (with mean arterial pressure < 65 mm Hg or needing pressors)  Yes  No

Significant Bleeding (Required IR, Surgery or >3u pRBCs)  Yes  No

Diagnosis of new pneumonia  Yes  No

**Vital signs (Record highest and lowest values since randomization; If only one value, record as lowest and check the "Single" box.**

Systolic BP: Lowest:    Highest:    mm Hg Single

Diastolic BP: Lowest:    Highest:    mm Hg Single

CVP: Lowest:   Highest:   cm H2O CVP not available  Single

Mean arterial pressure: Lowest:    Highest:    mm Hg Single

--	--	--	--	--	--	--	--	--	--

SITE ID PATIENT ID LETTER CODE

Record date / /  and time  of randomization  
MONTH D D Y Y Y Y TIME (0-2400)

Check box in first column of table below indicating randomization time.

Record date / /  and time  cooling started or check Not Cooled   
MONTH D D Y Y Y Y TIME (0-2400)

For each 2 hr block from randomization until 0800 of DAY AFTER randomization record highest and lowest temperature and lowest SpO2 and the FiO2 and Mean Airway Pressure measured closest to the SpO2 reading. If only one temperature measurement for block, enter in "Low" field and check box. If no SpO2 value for block, check "None" box.

Check box indicating randomization time	Time period	Temp (°C) If only one value record as "Low" and check box	Site of Temp measurement	Low SpO 2 (%) *	FiO 2 (%)	Mean airway pressure (cm H 2 O)
Day of Randomization						
	0001 to 0200	High: _____ Low: _____ 	 Esophageal  Urinary  Peripheral  IV	None 		

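### The daily bradycardia tick has no heart-rate criterion and the daily forms have no heart-rate field, so the count cannot be verified from the case report forms

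*Protocol*

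**What the plan says.** **Heart rate as a study measurement.** Section 7.1 opens its list of vital signs with "Heart rate, Blood Pressure, Respiratory rate, Pulse oximetry, Core temperature" and says that they are recorded as the study's data collection requires.

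**What the daily forms collect.** The Day 1 instruction (section 10.4) reads "Enter the lowest and highest values since randomization from the EMR for systolic and diastolic blood pressure and mean arterial pressure in mm Hg", and then asks for central venous pressure. Sections 10.5 to 10.7 and the vital-sign blocks of the Day 1, 3, 4 and 7 forms in the Appendix hold the same four quantities.

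**The bradycardia item.** Day 1 line 18, Day 3 and Day 4 line 17, and Day 7 line 13 carry the tick "Bradycardia (with mean arterial pressure < 65 mm Hg or needing pressors". The instructions are "On line 18, please if indicate if any of the adverse events occurred since randomization" for Day 1 and "On line 17, please if indicate if any of the adverse events occurred in the last 24 hours" for Days 2 and 3. Both ask for Yes or No and add no definition.

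**The only heart-rate figure for bradycardia.** Section 8 lists, among the criteria for ending hypothermia early, "persistent severe bradycardia (heart rate < 30 associated with mean arterial pressure <65 without vasopressor agents". Section 11 repeats it as a risk that leads to early termination.

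**Ventricular arrhythmia.** Sections 8 and 11 name it beside bradycardia and bleeding. On the daily forms it appears as "Intractable ventricular arrhythmia", a reason for discontinuing cooling.

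**Role of safety.** Section 1.1 makes safety measures part of the primary outcome and says that blinding is not possible. The SAP compares serious adverse events by chi-square.

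**The concern.** Bradycardia is one of three cooling harms that the protocol names, and one of three events that the daily forms solicit from both arms. A solicited event helps a between-arm comparison when two people looking at the same patient would tick the same box, or when a recorded value can settle a disagreement. Here the item has no rate and the forms hold no rate. The staff who tick it know which patients are being cooled.

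The count also has a use beyond description. Section 2.2.3.2 says that adverse events outside the individually reviewed categories are only tabulated unless a difference between the groups prompts a review of cases. If the daily ticks feed that tabulation, an inconsistent count makes the trigger less dependable. The pilot exists to decide whether COVID-19 patients can safely enter the larger trial, so this is information that the sponsor will want to trust.

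**Working it through.** The documents give no figure to reproduce. The check compares what a bradycardia count needs with what each form supplies.

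**Step 1. Where heart rate is recorded.**

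| Place | Heart-rate value? |
|---|---|
| Baseline form, lines 11 and 25 | Yes |
| Day 1 form, line 19, and section 10.4 | No |
| Day 2: shared Day 2/3 instructions, section 10.5 (form not in the text available) | No in the instructions |
| Day 3 form, line 18 | No |
| Day 4 form, line 18, and section 10.6 | No |
| Day 7 form, line 14, and section 10.7 | No |
| Time-block tables, Days 1, 3, 4 and 7 | No: SpO2, FiO2 and mean airway pressure, plus temperature on Days 1, 3 and 4 |
| Unassisted Breathing Checklist | Mentions a rise in heart rate as a distress sign; records no value |

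**Step 2. The components of the event.** Three are needed: heart rate, mean arterial pressure and vasopressor use. The Day 1, 3, 4 and 7 forms record the lowest pressure and the vasopressors given, each over the whole window. They do not record heart rate. The pressure and vasopressor entries are not tied to the moment of slowest heart rate, so the event cannot be rebuilt from the form.

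**Step 3. The two wordings side by side.**

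| | Daily tick | Sections 8 and 11 |
|---|---|---|
| Purpose | Solicited event, both arms | Early termination of cooling; risk description |
| Heart rate | None given | Below 30 |
| Mean arterial pressure | Below 65, as one alternative | Below 65, required |
| Vasopressors | Needing them is the other alternative | Without them |

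No instruction links the two columns, and they differ on vasopressors. The passages must be reconciled.

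**Step 4. Ventricular arrhythmia.** The daily event list has bradycardia, significant bleeding and new pneumonia. Arrhythmia is on Day 1 line 13 and on Day 3 and Day 4 line 12, as a reason for stopping cooling. A patient outside the hypothermia group skips those lines.

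**Step 5. Size.** Section 1.1 plans 20 patients and section 3.3 allocates 1:1, so 20 / 2 = 10 per arm, assuming equal arms. One patient classified differently moves an arm's rate by 1 / 10 = 10 percentage points.

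As an illustration with assumed counts:

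- 4 of 10 against 0 of 10: uncorrected chi-square = 20 × (4×10 − 6×0)² / (10×10×4×16) = 5.00, p = 0.025.
- 3 of 10 against 0 of 10: 20 × (3×10 − 7×0)² / (10×10×3×17) = 3.53, p = 0.060.
- By Fisher's exact test, 5 against 0 gives p = 0.033 and 4 against 0 gives p = 0.087.

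One tick can carry such a comparison across 0.05. The plan schedules no test of this tick, so these p-values show sensitivity only.

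**The case against.** Four stronger readings are tempting, and the documents do not support them.

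- **That the protocol gives two contradictory definitions of one outcome.** Sections 8 and 11 state when to stop cooling and what risks exist. Neither claims to define the form item. A narrow stopping rule and a broader solicited event can coexist, and both can be read as bradycardia with haemodynamic effect. The vasopressor phrases are also open: needing pressors may mean pressors given for the bradycardia, in which case a patient on them for sepsis would not count. What stands is that the form does not say.
- **That bradycardia cannot be checked at all.** Heart rate is measured in routine care, daily values are taken from the electronic record, and source documents are kept. For 20 patients at one centre, retrieval is feasible. What stands is that no passage plans it.
- **That arrhythmia is captured in one arm only.** Site staff must record all adverse events, the Adverse Event form is open to both arms, and a general cardiac cause-of-death box mentions arrhythmia. A reason for stopping cooling can apply only to cooled patients. What stands is that no structured prompt asks about ventricular arrhythmia in controls.
- **That the primary analysis is undermined.** The SAP tests serious adverse events and does not name this tick, and seriousness is judged separately. What stands is that the tick is one of the few structured safety items behind an otherwise unspecified set of safety measures.

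Free-text adverse events and the box for stopping neuromuscular blockade because of bradycardia offer other routes to the event. Neither supplies a heart-rate criterion or a dedicated field for the rate.

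**Conclusion.** The point holds as a gap between section 7.1 and the daily forms, and as a solicited event that lacks its defining measurement. On the forms as written, the bradycardia count depends on unblinded judgement and cannot be confirmed without going back to the chart. Specific solicitation of ventricular arrhythmia is confined to the hypothermia arm.

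The consequence is modest but worth correcting before enrolment: 10 percentage points per patient classified differently, assuming 10 per arm. How many patients would be affected cannot be estimated from the documents. The conclusion rests on the visible Day 1, 3, 4 and 7 forms and their instructions; for Day 2 it rests on the shared instructions alone. It does not depend on which heart-rate figure is appropriate, and none is proposed here.

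**What to change.** 1. In the vital-sign block of the Day 1, 2, 3, 4 and 7 forms and their instructions, add the lowest heart rate in the window, with the concurrent mean arterial pressure and vasopressor use (Yes or No).
2. Have the sponsor reconcile the form wording with sections 8 and 11, and write one definition of the bradycardia event that states the heart rate, pressure and vasopressor conditions. Derive the event in both arms from the recorded values.
3. Add ventricular arrhythmia, as already named in sections 8 and 11, to the daily event list for both arms.

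The cost is one row and one tick box per daily form, and slightly more transcription from a record that staff already consult for blood pressure.

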### 2.2.3.2 DSM procedures

The Data Analysis and Management Core (DC) will be responsible for managing Data Safety Monitoring, including preparing reports for bi-annual review by [name]. The following is an initial plan for adverse event (AE) reporting, which will be modified and finalized based on discussions with the DSMB:

1. Clinical site staff will be responsible for recording all AEs on the appropriate CRF.
2. Any deaths, life-threatening events, or events that occur within the first three study days, including NMB, cooling and rewarming, and unexpected SAEs occurring in the first study week will be reviewed by [name] based on information provided by [name].
3. [name] will report the SAE, including his assessment of relatedness to study procedures, to the University of Maryland Baltimore IRB and [name] within 48 hours of discovery.
4. All other AEs will be tabulated without case-by-case review unless a difference between treatment groups calls for review of a group of cases.
5. [name] will submit monthly tabular reports of all SAEs and other RAEs to [name] and will submit tabular summaries of all AEs to [name] every 6 months.
6. Since this is a small pilot study, there are no plans for an interim analysis and early termination based on futility or proven benefit.

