### 6/ Study Visit Schedule/Schedule of Events (see Gantt chart below)

DAYS	-2	0	1	2	3	4	7	8-27	28	ICU DC	Hospital DC	60	90
Screening data, consent, enrollment, monitor for randomization	X												
Pregnancy test (F)		F											
Randomization, baseline data, start assigned temperature management		X											
Q2h vital signs (e.g. SpO2, mean airway pressure, core temperature)		X	X	X	X	X	X						
Temperature management protocol		X	X	X	X								
ABGs		A	A	A	A	A	A						
Basic metabolic panel, CBC (times per day)		2	2	2	2	2	1						
Blood sugars (times per day)		4	4	4	4	A	A						
Research blood sample collection		X	X	X	X	X	X						
Ventilator and respiratory parameters	X	X	R	R	R	R	R						
Fluid management		X	X	X	X	X	X						
NMB status	X	X	X	X	X	X	X						
Medication review (pressors, steroids, inhaled vasodilators)		X	X	X	X	X	X						

Monitor for AEs		X	X	X	X	X	X	X	X	x	x	X	X
Calculation 28-day VFDs, ICU-FDs									X				
MOCA										X	X		
Assess Vital and functional status		X	X	X	X	X	X	X	X	X	X	X	X

X = Required (time not specified)

A = When Available

R = Measured during daily reference measurements (0600-1000). When more than one value is available, the value obtained closest to 8 a.m. will be recorded.

F = Required on females of reproductive age.

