### Placing the order to initiate hypothermia:

- Order sedation to RASS >-4 and Nimbex to achieve 2 twitches on train-of-four testing.
- Enter UMMC MED-CC Hypothermia Following Arrest Supplemental order set in Epic with the following modifications:
  - i. De-select: Capnography, CVP monitoring, SvO2 monitoring, NPO, Bair Hugger, Maintain MAPBP > 80 mmHg, Document Water temperature, CXR, sodium chloride 0.9% bolus, fentanyl, and vecuronium, cisatracurium.
  - ii. Under Chemistry, select Comprehensive Metabolic Panel
  - iii. Modify Hyper/Hypothermia order by changing stop date from 24h to 48 h and changing comments to: "Lower patient's temperature to **34 – 35C** as quickly as possible per protocol. Maintain **core temperature between 34 and 35C for 48 hours**. AT **48 hrs** after the initial cooling, re-warm patient no faster than **0.3** degree C per hour to **36C**." Delete "Then maintain ≤ 37C for 48 hours." (Changes from Epic order set are underlined and bolded.) These instructions have been added to the Randomization CRF.

2. Usual Temperature Management Arm: Controls will receive sedation and NMB as clinically indicated to achieve synchrony with the ventilator. During the 54h post-randomization period (corresponding with cooling and rewarming in the TH arm), acetaminophen will be given for core temperature  $>38^{\circ}\text{C}$  and surface cooling initiated for core temperature  $>38.5^{\circ}\text{C}$  and adjusted to maintain temperature  $\leq 38^{\circ}\text{C}$ . If patients are hypothermic (core temperature  $<35.5^{\circ}\text{C}$ ), surface warming will be initiated to restore core temperature to  $37^{\circ}\text{C}$ . Following the 54h treatment period, temperature management in both arms will be directed by the ICU team.

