#### 10.12/ Adverse Event CRF

Refer to Section 12: Adverse Event Reporting

- Record site ID code, 3-digit study ID, and the unique 3 letter identifier in the indicated fields at the top of each page.
- Indicate on line 1 whether the patient had any adverse event (AE) by checking the appropriate “Yes/No” box.
- If “Yes,” fill out one column for each adverse event.

- In row 2 give a brief description of the AE.
- In row 3, record the name of the individual entering data about the AE.
- Record the date and time the AE was first detected in rows 4 and 5, respectively. If unknown, check the “?” box.
- Record the date and time the AE was resolved in rows 6 and 7, respectively. If unknown or if not resolved check the “?” box.
- Indicate the most appropriate severity grade of the AE by checking the appropriate box in row 8 (check only one box).
- Indicate whether the AE was serious by checking the appropriate “Yes/No” box in row 9.
- Indicate whether the AE was expected by checking the appropriate “Yes/No” box in row 10.
- Indicate likelihood of relatedness to the study intervention by checking the appropriate box in row 11 (check only one box).
- Indicate the action taking with the study intervention by checking the appropriate box in row 12 (check all that apply).
- Indicate other actions taken by checking the appropriate box in row 13 (check all that apply).
- Record the outcome by checking the most appropriate box in row 14 (check only one box).
- Enter the name of the investigator who made the assessment about severity and study relatedness in row 15.
- Enter the date of the assessment in row 16.

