## 11./ Study Associated Risks and Risk Mitigation

a./ Although not expected to occur with modest TH to 34°-35°C, patients can develop:

b./ (1) persistent severe bradycardia (heart rate <30 associated with mean arterial pressure <65 without vasopressors); (2) uncontrolled bleeding and (3) intractable ventricular arrhythmias, there. In the event any of these conditions happens, TH protocol will be early terminated following clinical guidelines.

(4)There is a slightly Increased risk of infection, study subjects are closely monitored for infection and the appropriate use of antibiotics should be initiated as standard of care; (5) there is a mild risk of changes in fluid and chemical balance, this patient population is closely monitored and correction is implemented as standard of care; (5) there is a mild to moderate risk of hyperglycemia occur, this patient population is closely monitored and correction should be implemented as standard of care; (6) there is a slight reduction in the ability of blood clotting mechanism, this patient population is closely monitored and corrections should be implemented as standard of care.

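### Infection, a named cooling risk, is asked about only through an undefined pneumonia box, and because the fever cue differs between arms for about 54 h, detection may differ by arm in an unknown direction

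*Protocol*

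**What the plan says.** **The risk.** Protocol Section 11 lists infection among the risks of cooling: "There is a slightly Increased risk of infection, study subjects are closely monitored for infection". Treatment is left to standard care.

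**The solicited item.** On the daily forms in the Appendix the only infection question is a Yes/No box, "Diagnosis of new pneumonia" (Day 01 line 18, Day 03 and Day 04 line 17, Day 07 line 13). It has no criteria. Section 10.4 adds only the instruction "please if indicate if any of the adverse events occurred since randomization". The items beside it are defined. Bleeding reads "Significant Bleeding (Required IR, Surgery or >3u pRBCs", and bradycardia is tied to a blood pressure threshold or pressor need. No daily form has a field for cultures, antibiotics, or bloodstream, line or urinary infection.

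**The open route.** Section 2.2.3.2 states: "Clinical site staff will be responsible for recording all AEs on the appropriate CRF". The adverse event form is free text; Section 10.12 says "In row 2 give a brief description of the AE". The Section 6 schedule marks "Monitor for AEs" from day 0 to day 90.

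**Temperature.** Under Section 8 the hypothermia (TH) arm is held at 34-35°C for 48 h and then rewarmed to 36°C. For the 54 h after randomization, in controls "acetaminophen will be given for core temperature" above 38°C. Surface cooling starts above 38.5°C and aims for 38°C or less. After that the ICU team directs temperature in both arms, and the protocol includes no fever suppression after cooling.

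**Analysis.** The SAP plans a chi-square test on SAEs and names no infection comparison.

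**The concern.** Every patient enters with bilateral infiltrates and care is unblinded, so calling a pneumonia new is a bedside judgement. Fever is one of the cues for that judgement and for sending cultures. During the temperature-control window it cannot appear in the TH arm, but it can in controls. It is a common cue: the reanalysis in Section 1.3 found fever in 65% of ARDS patients within three days.

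The open adverse event form does not remove the problem, because an entry there also needs someone to suspect infection first. Section 2.2.1.1.1 tabulates events outside the serious and reportable categories without case review unless the arms differ. Unequal detection could hide exactly that difference. The pilot is meant to decide whether COVID-19 patients can safely enter the Phase IIb trial, so counts of a named harm should at least be interpretable.

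**Working it through.** The documents give no infection rate and no detection rate, so there is no plan figure to reproduce. The window arithmetic below uses the forms. The case counts rest on stated assumptions.

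**1. Time the pneumonia box covers.** The Day 1 form covers 8 h 1 min to 31 h 59 min (Appendix, note after the randomization form), taken as 8 and 32 h. Days 2, 3 and 4 cover 24 h each, and Day 7 covers the prior 24 h. The Day 2 form is not reproduced in the public copy. Section 10.5 gives shared instructions for Days 2 and 3, so I take it to match.
- Shortest: 8 + 72 + 24 = 104 h
- Longest: 32 + 72 + 24 = 128 h

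**2. Share under protocol temperature control (54 h).**
- 54/104 = 51.9% and 54/128 = 42.2%
- Asked time after the window: 104 - 54 = 50 h to 128 - 54 = 74 h

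**3. Time not asked.** The Day 4 form closes 8 + 72 = 80 h to 32 + 72 = 104 h after randomization. The Day 7 look-back opens 48 h later. The gap therefore begins 80 - 54 = 26 h to 104 - 54 = 50 h after temperature control ends. It is the same in both arms.

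**4. What unequal detection could do.** Expected recorded cases = n × true risk × detection, with n = 10 (20 patients, 1:1). All risks and detection rates are assumed.

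| True risk, TH / control | Detection, TH / control | Recorded, TH / control |
|---|---|---|
| 40% / 20% | 100% / 100% | 4.0 / 2.0 |
| 40% / 20% | 75% / 100% | 3.0 / 2.0 |
| 40% / 20% | 50% / 100% | 2.0 / 2.0 |
| 20% / 20% | 50% / 100% | 1.0 / 2.0 |
| 20% / 20% | 100% / 75% | 2.0 / 1.5 |

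The last row is the reverse case, in which staff look harder in the TH arm.

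**5. Masking confined to its window.** Suppose detection in TH is halved only during the 54 h, infections are spread evenly over the asked time, and missed ones are never picked up later. Overall detection is then 1 - 0.5 × share.
- 1 - 0.5 × 0.519 = 0.740, giving 10 × 0.40 × 0.740 = 2.96 cases
- 1 - 0.5 × 0.422 = 0.789, giving 10 × 0.40 × 0.789 = 3.16 cases

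So a true 4.0 versus 2.0 would be recorded as about 3.0 to 3.2 versus 2.0.

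**6. What a test could show with perfect detection.** Exact enumeration of all 10-versus-10 tables at two-sided 0.05 gives this power:
- 40% versus 20%: about 13% (uncorrected chi-square), 6% (Fisher)
- 60% versus 30%: about 25% (uncorrected chi-square), 12% (Fisher)

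**The case against.** A reader might infer three stronger claims, and the documents support none of them.

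- **That infection is captured only by the pneumonia box.** It is not. All adverse events must be recorded, the adverse event form takes any event, and severe sepsis is a listed cause of death. The box is the only infection item that the daily forms solicit.
- **That fever is removed in the TH arm only.** Controls also receive protocol fever treatment over the same 54 h. What remains is a difference in degree: no fever in TH, against treatment that starts above 38°C in controls.
- **That the comparison is biased towards missing TH infections.** This is plausible but not shown. About half or more of the asked time lies outside the window, so an infection masked early may be diagnosed and ticked later. White cell count, oxygenation and vasopressor need are still recorded. Because the trial is open-label and names infection as a cooling risk, staff could also look harder in the TH arm. The absence of prompts for other infections applies equally to both arms.

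It is also fair that the SAP plans no infection test and that about 10 per arm could not settle the question even with perfect detection. That weakens any claim that the trial's formal result is at stake. It does not weaken the case for interpretable counts, since description is all that this sample can offer.

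**Conclusion.** The point holds as a modest weakness in measurement. The daily forms solicit a named harm only through an undefined box. The fever cue differs between arms for 54 h, which is 42% to 52% of the asked time, and 48 h on days 5 and 6 are not asked at all. Detection may therefore differ by arm.

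Its direction and size cannot be known from the documents. The case counts above depend wholly on assumed risks and detection rates, and the row in which a doubling vanishes needs halved detection over the whole period. The window figures assume that the Day 2 form matches Day 3. Given the small sample, an infection result showing no difference should not be read as evidence of no excess. Better recording is a cheap improvement here; its absence does not invalidate the pilot.

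**What to change.** **Forms.** Keep the pneumonia tick on the Day 1, 2, 3, 4 and 7 forms and add, for both arms and abstracted from the medical record:
- the date and site of each new positive respiratory, blood or other culture;
- the start date of any new antibiotic course for suspected infection;
- the number of cultures sent.

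Let these items and the tick on the Day 7 form cover days 5 to 7. That form already looks back 72 h for hypothermia and proning (lines 9 and 19).

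**Definition.** Do not use temperature as a criterion. Do not require a positive culture for every event: that would drop culture-negative pneumonia and still depend on who was cultured. Show culture-positive events and antibiotic-treated, culture-negative events separately.

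**SAP.** Add that infections will be reported descriptively by arm beside the number of cultures sent. State that culture and antibiotic data may still reflect fever-prompted testing, so a null result is not evidence of no excess. Culture counts make unequal testing visible; they do not correct it.

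**Cost.** A little more chart review for 20 patients. No new tests are asked for and clinical management does not change.
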